## Protocol Synopsis

Protocol Title:	Cold Stored Platelet Early Intervention - TBI (CriSP-TBI) Trial
Protocol Number:	STUDY20070044
NCT Number:	NCT04726410
Version # and Date:	Version 12 dated 02/08/2023
Investigational Drug:	Cold Stored Platelets (CSP)
Clinical Phase	Phase II
Funding Agency	Department of Defense
IND Sponsor:	[name], MPH
Principal Investigator:	[name], PhD
Research Facility	UPMC Presbyterian Hospital
Study Aims:	
AIM#1: Determine the feasibility, most appropriate study population and primary outcome that will lead to a large multicenter clinical trial designed to evaluate the effectiveness of cold stored platelet early intervention in patients with TBI requiring platelet transfusion.
 
AIM#2: Determine whether early cold stored platelet infusion compared to standard platelet transfusion results in improved clinical outcomes and hemostatic function in patients with traumatic brain injury requiring platelet transfusion.
 
AIM#3: Determine if early cold stored platelet hemostatic function is similar at 1 through 7 days as compared to 8 through 14 days in patients with TBI on antiplatelet therapy.

Study Design:	Open label, single center, randomized trial designed to determine the feasibility, efficacy and safety of urgent release cold stored platelets in blunt injured patients with traumatic brain injury requiring platelet transfusion.
Planned Sample Size:	100 subjects with TBI
Planned Study Time:	3-year study with 2 years of enrollment
Major Inclusion Criteria:	
Patients with traumatic brain injury, defined by presence of potential progressive intracranial injury on CT scan imaging, at significant risk for urgent neurosurgical procedure as determined by neurosurgical evaluation, who meet at least one of the following:
 
 
History or indication of pre-injury oral antiplatelet agent use
 
Need for platelet transfusion per standard practice
 

Major Exclusion Criteria:	
 
Wearing NO CriSP opt out bracelet
 
Hypotension in ED (SBP< 90 mmHg)
 

	
 
3. Age > 89 or < 18 years of age
 
4. Penetrating injury
 
5. Prisoner
 
6. Pregnancy
 
7. Going to operating room for non-neurosurgical intervention in first 60 minutes
 
8. Platelet transfusion contraindicated per care team (for example, recent vascular stent, embolic stroke, intracranial and/or vascular lesions)
 
9. Objection to study voiced by participant or family member in Emergency Department
 
10. Currently on therapeutic anticoagulant in addition to aspirin and/or clopidogrel (e.g. warfarin, direct-acting oral anticoagulants)
 

Primary Endpoint:	Feasibility
Secondary Endpoints:	
 
• 24-hour mortality
 
• GOSE at 6 months
 

## Specific Aims

Platelet transfusion is commonly provided early after injury in patients with traumatic brain injury (TBI) to reverse antiplatelet medications (aspirin, Plavix). Taking antiplatelet medications potentially worsens intra-cranial hemorrhage and outcomes following TBI. Importantly, other antiplatelet medications such as NSAIDs have also been shown to inhibit platelet aggregation and compromise coagulation at doses commonly taken by warfighters. Whether current standard care room temperature (RT) platelet transfusion adequately reverses platelet inhibition and improves outcomes following traumatic brain injury remains poorly characterized. Cold stored platelets may provide better hemostatic correction and improve outcomes in patients with TBI requiring platelet transfusion.

Platelet use in far forward environments are not available due to logistical storage and shelf-life requirements. Cold-stored platelets can be refrigerated like red blood cells and plasma units and may be less prone to bacterial contamination. Growing evidence suggests that cold-stored platelets have superior hemostatic capabilities. For patients with brain injury, cold stored platelets may be beneficial in an urgent release fashion soon after arrival to the trauma center as compared to current standard care. Currently there is no high-level clinical trial evidence demonstrating the safety and efficacy of urgent release cold stored platelet transfusion following injury. The aims of the Cold Stored Platelet early intervention TBI (CriSP-TBI) pilot trial are to determine the feasibility, efficacy and safety of urgent release cold stored platelets in patients with traumatic brain injury requiring platelet transfusion.

**AIM#1:** Determine the feasibility, most appropriate study population and primary outcome that will lead to a large multicenter clinical trial designed to evaluate the effectiveness of cold stored platelet early intervention in patients with TBI requiring platelet transfusion.

**AIM#2:** Determine whether early cold stored platelet transfusion compared to standard platelet transfusion results in improved hemostatic function and clinical outcomes in patients with traumatic brain injury requiring platelet transfusion.

**AIM#3:** Determine if early cold stored platelet hemostatic function is similar at 1 through 7 days as compared to 8 through 14 days in patients with TBI on antiplatelet therapy.

Hypothesis for clinical outcomes: Early infusion of cold stored platelets as compared to standard platelet transfusion will result in improved 6 month Extended Glasgow Outcome Scale (GOS-E), lower 24 hour and in-hospital mortality, a lower need for craniotomy/craniectomy, lower need for ICP monitoring, a lower rate of TBI progression, improved hemostatic function, reversal of platelet inhibition and a similar rate of allergic/transfusion reactions and incidence of transfusion related acute lung injury in patients with TBI requiring platelet transfusion.

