Capacity to provide informed consent will be assessed prior to randomization and will primarily be determined by Glasgow Coma Scale (GCS). Potential subjects with a GCS of less than 15 will be considered unable to consent. Potential subjects with a GCS of 15 will undergo a GOAT assessment, performed by a study investigator or neurosurgery CRC. A score of 74 or below will be considered unable to consent. For subjects that are determined to be unable to consent, assent will be obtained when applicable. The study team will also attempt to identify an appropriate LAR to provide prospective informed consent. If a LAR is identified within the 2-hour period after initial CT scan in the ED, this individual will be approached for proxy consent. If not, the patient will be enrolled under EFIC. If a potential subject has a GCS of 15 and scores 75 or above on the GOAT, we will presume s/he is capable of providing direct informed consent and will seek to obtain informed consent via a physician investigator.

VerifyNow Measurements: When feasible, VerifyNow-Aspirin and VerifyNow-P2Y12 measurements for patients with a history of aspirin and/or clopidogrel, respectively, may be performed prior to platelet transfusion and for response monitoring following initial platelet transfusion. However, need for platelet transfusion will be determined by neurosurgical and/or trauma surgery recommendations. VerifyNow measurements will only be obtained when feasible. Measurement cut points for determining platelet inhibition will follow manufacturer guidelines <https://www.werfen.com/na/en/verifnow> .

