**Study Intervention:**

**Study Intervention Arm:** Patients randomized to the intervention arm will receive an early infusion of urgent release cold stored platelets (CSP) once the patient is determined to meet all inclusion and no exclusion criteria. When clinically feasible, patients will undergo VerifyNow Aspirin or P2Y12 testing following initial platelet transfusion. Those patients who have not increased their respective ARU or PRU measurements to levels consistent with no drug effect (ARU > 550; PRU > 220), or who have another clinical indication for additional platelet transfusion, may undergo a second CSP infusion.

CSP infusion will occur once IV access is obtained irrespective of location. CSP infusion should be initiated first when possible but can be infused concomitantly with other transfusion requirements including packed red blood cells, plasma, or whole blood per institutional standard care. The administration will be begun by clinical staff.

**Standard Care Arm:** Patients randomized to the standard care arm will receive room temperature (RT) platelet transfusion per standard care at the University of Pittsburgh once the patient meets all inclusion and no exclusion criteria. When clinically feasible, patients will undergo VerifyNow Aspirin or P2Y12 testing following initial platelet transfusion. Those patients who have not increased their respective ARU or PRU measurements to levels consistent with no drug effect (ARU > 550; PRU > 220), or who have another clinical indication for additional platelet transfusion, may undergo a second RT platelet infusion.

**Randomization and Masking:** Individual patients determined to meet all inclusion and no exclusion criteria in the emergency department will be randomized and assigned according to a 1:1 ratio to CSP infusion or standard care using a permuted block design with variable block sizes of 4 and 6. The arm assignment will be provided in real time at the individual patient level by accessing an electronic randomization system. Backup envelopes containing randomization assignments will be available by contacting the Data Coordinating Center should there be any issues or failure of the electronic randomization system. Trauma and Neurosurgical attending and ED physicians will not be masked to treatment assignment as the study intervention is a blood product and full traceability is required. Arm assignment will be concealed to all outcome assessors performing the GOSE during follow-up.

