## Outcomes

**Primary Outcome:** The primary outcome for this pilot trial will be feasibility. Secondary performance and feasibility outcomes will include the proportion of eligible patients that can be randomized, 2) the proportion of eligible patients who are enrolled in the trial, 3) proportion of enrolled patients which adherence to the study protocol, and 4) proportion of enrolled patients who complete study follow-up.

**Secondary Outcomes:** Our principle secondary clinical outcome for the proposal will be 6-month Extended Glasgow Outcome Scale (GOS-E). Additional secondary outcomes will include 24-hour mortality, in-hospital mortality, need for craniectomy/craniotomy, need for ICP monitoring, TBI progression based upon serial CT imaging in initial 24 hours, Galveston Orientation and Amnesia Test (GOAT score) at discharge, incidence of allergic/transfusion reaction, incidence of transfusion related acute lung injury (TRALI), measurements of platelet hemostatic function, and incidence of thromboembolic events.

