**Platelet Hemostatic Function:** Once randomized, blood sampling for platelet hemostatic function prior to platelet transfusion irrespective of arm assignment will be performed if clinically feasible. Following each platelet transfusion, further assessment of platelet hemostatic function may be performed (up to 2 times). Platelet hemostatic function will be assessed by TEG analysis and TEG with platelet mapping. Whole blood aggregometry and flow cytometry will be performed when feasible across both arms.

**Thromboembolic events:** Pulmonary embolism, venous thrombosis, or arterial thrombosis that occurs during the primary admission hospital stay will be documented for all enrolled patients. Radiographic confirmation via CT imaging, transthoracic or trans-

esophageal echo, or ventilation/perfusion scanning will be required. Presumed or clinical suspicion for an embolic event that is unable to be verified radiographically will also be documented.

**Severity Stratification:** TBI characteristics will be recorded and based upon CT imaging results (classification: subarachnoid, subdural, intracerebral hemorrhage, epidural, +/- shift, multifocal) and TBI severity will be characterized by presenting GCS, Abbreviated Injury Severity (AIS) coding and Rotterdam CT scores.

**Predefined Subgroups:** Predefined subset analyses for the TBI cohort will be performed looking at 1) patients who did or did not receive a craniectomy/craniotomy, 2) patients who did or did not require ICP monitoring, 3) patients arrived from the scene of injury versus those brought from a referral hospital; 4) patients with a pre-injury history of aspirin use as compared to clopidogrel use; 5) CSPs with shelf time of 1 to 7 days as compared to 8 to 14 days. It is recognized that the study is not appropriately powered for these subgroup comparisons and the results and conclusions formulated from these subgroup analyses will be considered exploratory in nature and will not be used as a basis for treatment recommendations.

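### Reversal of platelet inhibition is hypothesised to differ between arms, but no outcome, definition or analysis says what reversal is or uses the VerifyNow results

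*Combined protocol and SAP*

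**What the plan says.** All references are to the combined protocol and SAP.

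- **Hypothesis (Specific Aims).** The list of expected benefits includes "improved hemostatic function, reversal of platelet inhibition and a similar rate of allergic/transfusion reactions". Hemostatic function and reversal are separate items.
- **Endpoints (Protocol Synopsis; Outcomes).** The synopsis names 24-hour mortality and 6-month GOSE as secondary endpoints. The fuller list under Outcomes ends with "measurements of platelet hemostatic function, and incidence of thromboembolic events". Neither list names reversal.
- **Definition (Secondary Outcome Definitions).** "Platelet hemostatic function will be assessed by TEG analysis and TEG with platelet mapping". In addition, "Whole blood aggregometry and flow cytometry will be performed when feasible across both arms". Sampling is before transfusion if clinically feasible, and possibly after each transfusion, up to two times. VerifyNow is not among the assays.
- **VerifyNow Measurements paragraph.** For patients with a history of aspirin or clopidogrel, the tests "may be performed prior to platelet transfusion and for response monitoring following initial platelet transfusion". However, "VerifyNow measurements will only be obtained when feasible". On thresholds: "Measurement cut points for determining platelet inhibition will follow manufacturer guidelines".
- **Study Intervention.** In the same wording for both arms, patients whose values have not risen to "levels consistent with no drug effect (ARU > 550; PRU > 220"), or who have another clinical indication, may have a second unit of the assigned product.
- **Statistical Analysis Plan.** Binary outcomes get a chi-square test and then logistic regression adjusted for baseline GCS. Continuous outcomes get a t-test and then analysis of covariance adjusted for baseline GCS. VerifyNow, ARU, PRU and reversal are not mentioned.
- **Data Management.** The in-hospital data list covers the primary and secondary outcomes but does not name VerifyNow, ARU or PRU.

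**The concern.** Specific Aims gives reversal of antiplatelet drugs as the reason platelets are transfused in this population, and says it is poorly characterised whether room temperature platelets achieve it. A between-arm hypothesis on that question, with no endpoint behind it, leaves the assay, the time point and the threshold to be chosen once the data are in. Followed as written, the plan yields no prespecified statement of how often either product reversed the drug effect. Aim 1 is to choose the population and primary outcome for a larger trial, and such a figure would be direct planning information.

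Two features of the present rules add to the problem. A second unit may be given because the first did not reverse inhibition, so an assay read after the last unit mixes the effect of the product with the number of units. Continuous assay values are also adjusted for baseline GCS but not for the patient's own pre-transfusion value.

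**Working it through.** No figure in the plan bears on this point. Its precision table concerns feasibility proportions, and its one power statement concerns GOSE. The main check is therefore a reading of the text, followed by arithmetic on what the proposed outcome could deliver.

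**Step 1: trace the hypothesis through the plan**

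| Place | Reversal defined? | VerifyNow used? |
|---|---|---|
| Hypothesis, Specific Aims | Named, not defined | No |
| Synopsis endpoints | No | No |
| Outcomes, secondary list | No | No |
| Platelet Hemostatic Function definition | No parameter, threshold or analysis time point | No |
| VerifyNow Measurements | Refers to manufacturer cut points for inhibition | Optional, before and after first transfusion |
| Study Intervention | No-drug-effect levels given | In the text on a possible second unit |
| Statistical Analysis Plan | No | No |
| Data Management | No | No |

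The only numerical no-drug-effect levels in the document belong to the assay that is absent from the outcomes, the analysis and the data list.

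**Step 2: precision of a difference in reversal proportions**

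Inputs: about 50 patients per arm (sample size section). The share with usable paired VerifyNow results is not stated, so the number evaluable per arm, n, is an assumption shown as a range. Proportions near 0.50 in both arms are also assumed; this gives the widest interval.

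95% CI half-width = 1.96 × √(2 × 0.25 / n)

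- n = 15: 1.96 × √0.0333 = 0.36
- n = 20: 1.96 × √0.0250 = 0.31
- n = 30: 1.96 × √0.0167 = 0.25
- n = 45: 1.96 × √0.0111 = 0.21
- n = 50, the ceiling if every patient were evaluable: 1.96 × √0.0100 = 0.20

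**Step 3: detectable contrast, as illustration**

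Two-sided alpha 0.05, power 80%, equal arms. For control proportion p₁ and CSP proportion p₂ with mean p̄, solve for p₂ in

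n = [1.96√(2p̄(1−p̄)) + 0.842√(p₁(1−p₁) + p₂(1−p₂))]² / (p₂−p₁)²

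For a continuous value the detectable difference is (1.96 + 0.842) × √(2/n) SD. The control proportions of 0.30 and 0.50 are assumptions.

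| n per arm | p₂ if p₁ = 0.30 | p₂ if p₁ = 0.50 | Continuous, SD units |
|---|---|---|---|
| 50 | 0.57 | 0.77 | 0.56 |
| 35 | 0.63 | 0.81 | 0.67 |
| 25 | 0.69 | 0.86 | 0.79 |
| 15 | 0.79 | 0.94 | 1.02 |

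Only large differences could be detected, so the outcome should be an estimate with its interval and not a test.

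**The case against.** The strongest reply is that platelet function is already an outcome. It may be sampled before and after transfusion, includes TEG with platelet mapping, and falls under the general rules for continuous and binary outcomes. Aim 2 speaks only of hemostatic function and clinical outcomes, so reversal could be read as part of that. This stands in part. A reader might infer that inhibition goes wholly unanalysed, and the documents do not support that. What they lack is a reversal criterion, a reading tied to the first unit, and adjustment for the pre-transfusion value.

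Three other inferences also go too far.

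- *VerifyNow serves only to decide on a second unit.* The VerifyNow paragraph also gives it the purpose of monitoring response. The exact statement is that no analysis is specified. Descriptive reporting is not ruled out.
- *The paired data will be there anyway.* Testing is permitted, not required. The arm descriptions mention only the post-transfusion test, and the data list does not name the values.
- *Most of each arm will be evaluable.* A patient must have taken aspirin or clopidogrel (the second inclusion route does not require it), be inhibited before transfusion, and have both tests, the second before any further unit. The documents give no basis for any particular number.

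It is also fair to say that a subset chosen by optional tests, in a trial with unmasked clinicians, is not a clean randomised comparison. That argues for an exploratory label and reporting of test availability. It does not argue for leaving the hypothesis without a definition. Aggregometry and flow cytometry are also done only when feasible, yet they sit within an outcome definition.

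**Conclusion.** The point holds in this form: the plan states a between-arm hypothesis of reversal and gives no outcome, definition or analysis that would report it, while platelet mapping addresses it only in part. The finding itself rests on the text and needs no numerical assumption.

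The value of the remedy depends on an unknown number. Under the assumption of proportions near 50%, the half-width runs from about 0.36 at 15 evaluable per arm to 0.21 at 45. At the lower end the result is descriptive and imprecise, so usefulness for planning the larger trial cannot be promised. This is a secondary, exploratory matter. The feasibility primary outcome, the sample size and the GOSE analysis are unaffected.

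**What to change.** 1. **Outcome.** Add an exploratory secondary outcome to Outcomes and Secondary Outcome Definitions. Population: patients on aspirin and/or clopidogrel whose pre-transfusion VerifyNow value shows inhibition. Measure: the proportion reaching the protocol's stated no-drug-effect level after the first unit and before any second.
2. **Analysis.** Compare by randomised arm as a risk difference with 95% CI. Analyse ARU and PRU separately, and state how patients on both drugs count.
3. **Adjustment.** Add analysis of covariance of the post-first-unit value on arm and pre-unit value. Adjust the continuous assays already listed under Platelet Hemostatic Function for their own pre-transfusion values in the same way.
4. **Data.** Add ARU and PRU values, with times relative to each unit, to the case report form and the data list.
5. **Cut points.** Use them for analysis only. Confirm that the values under Study Intervention agree with the manufacturer guidelines cited under VerifyNow Measurements, and reconcile the two places if they do not. No clinical rule needs to change.
6. **Missing tests.** Report test availability by arm and the number evaluable, and label the comparison exploratory.

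If the sponsor does not want this outcome, the hypothesis item should be deleted, or the plan should say which listed assay addresses it and by what criterion.

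The cost is SAP and case report form wording, with no new assay. The drawback is that optional testing and unmasked clinicians make this a selected subset, and reporting missingness discloses that selection without removing it.

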A two-sided Chi-square test will be used to compare the distribution of the GOS-E between the treatment arms. An ordinal polytomous regression model will then be used to assess the independent impact of CSP on GOS-E after controlling for potential confounding effects of baseline characteristics which reveal imbalance between treatment groups. The analytic approach for the secondary trial outcomes will vary based on the type of outcome. For binary outcomes, a two-sided Chi-square test for proportions will be used to compare the proportions between those receiving and not receiving CSP. A logistics regression model will then be used to assess the independent impact of CSP on the secondary trial outcomes while adjusting for baseline GCS. For time-to-event outcomes (e.g., time to death), Kaplan-Meier curves will be generated for each treatment group and a log-rank test will be used to compare the distribution of the cumulative proportion. A Cox-proportional hazards regression model will be used to assess the independent impact of CSP on time to death after controlling for baseline GCS. For continuous outcomes a two-sided t-test for means will be used to compare the means between those receiving and not receiving CSP. An analysis of covariance model will be used to assess the independent effect of CSP. after controlling for baseline GCS .

Analyses to test for the homogeneity of the treatment effect will be carried out for the pre-defined subgroups. Regression models appropriate for the outcome variable (e.g., logistic regression for binary outcome variables) will stratified by the pre-defined subgroups. Estimate of the treatment effect (odds ratio) and 95% confidence interval will be generated for each model and displayed on a forest plot.

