Secondary analyses will be conducted to assess the impact of age of the CSP on outcomes. These analyses will be carried out among those who are randomly assigned to the CSP group and the impact of the age of the CSP on outcomes will be evaluated. Since the sample will not be randomly assigned, it will be important to adjust for potential confounding effects. A propensity score will be generated as an indicator of the age of the CSP ( $\leq 7$  days vs.  $> 7$  days). Multivariable regression models will be used to assess the independent relationship of age of the CSP on outcome. The model type will vary based on the outcome (e.g., logistic regression for binary variables). Each model will include a fixed main effect for the indicator of the age of the CSP as well as an inverse probability weight for the propensity of getting CSP  $\leq 7$  days of age.

**Sample Size Justification and Power Analysis (n=100):** For the enrollment, adherence and event rates needed for planning and feasibility analyses, we calculated the two-sided 95% CI for proportions ranging from 0.70 to 0.90. For example, a sample size of 100 produces a two-sided 95% CI of 0.82 to 0.95 when the sample proportion is 0.90. When the sample proportion is .70, the two-sided CI is 0.60 to 0.82. These confidence intervals are then repeated within the treatment arm.

Sample Size	Width	Proportion (P)	Lower Limit	Upper Limit
Full Sample				
100	0.19	0.700	0.60	0.82
100	0.17	0.800	0.71	0.87
100	0.13	0.900	0.82	0.95

One Treatment Arm				
50	0.27	0.700	0.55	0.82
50	0.24	0.800	0.66	0.90
50	0.19	0.900	0.78	0.97

For the principle secondary clinical outcome of the GOSE, based on a 2x8 (treatment x GOSE) there is 80% power to detect an effect size of 0.3788, assuming a type I error rate of 0.05, a two-sided alternative hypothesis, 7 degrees of freedom, and a sample size of 50 participants per treatment group.

**Randomization of Ineligible Participants:** It is anticipated that there will be a small proportion of patients enrolled who receive CSPs or standard care that in retrospect will not have met the entry criteria and are thus ineligible. In this circumstance, patients will be analyzed according to the group to which they were randomized. Subgroup analyses based on eligibility criteria will be performed if the number of patients so affected is large.

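### Similar rates of transfusion reactions and TRALI are hypothesised, but only a test of difference is planned and no criterion for similarity is given

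*Combined protocol and SAP*

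**What the plan says.** The paragraph on the hypothesis for clinical outcomes, under Specific Aims, lists what early cold stored platelets (CSP) are expected to do. The efficacy items are all hypothesised to improve or to be lower. For allergic/transfusion reactions and TRALI the hypothesis is instead "a similar rate of allergic/transfusion reactions and incidence of transfusion related acute lung injury". The Outcomes section lists both among the secondary outcomes.

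Under Analysis for Clinical Outcomes, the SAP gives one method for all binary outcomes: "For binary outcomes, a two-sided Chi-square test for proportions will be used to compare the proportions between those receiving and not receiving CSP". It continues: "A logistics regression model will then be used to assess the independent impact of CSP on the secondary trial outcomes", with adjustment for baseline GCS. Nothing separate is given for the two outcomes hypothesised to be similar. No section contains a margin, an equivalence or non-inferiority test, or a confidence-interval rule for them.

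The sample size section gives power for GOSE only, and precision only for single proportions from 0.70 to 0.90. It states no expected reaction or TRALI rate.

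**The concern.** The null hypothesis of the planned test is that the two rates are equal. Rejecting it is evidence of a difference. Failing to reject it is not evidence of sameness, because the same result arises when the data are too few to tell. The hypothesis and the test therefore point in opposite directions, and no outcome of the test can confirm the hypothesis.

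Safety is one of the declared aims of the pilot, and its results are meant to inform larger trials. The only between-arm output specified for these two outcomes is a p-value and a GCS-adjusted model. Confidence intervals for treatment effects are promised for the subgroup models but not for this main comparison. A reader of the results would have a p-value that does not show how large an excess of reactions or TRALI remains compatible with the data.

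**Working it through.** **Inputs from the documents**
- Allocation: patients are "assigned according to a 1:1 ratio to CSP infusion or standard care".
- Size: "a sample size of 50 participants per treatment group".
- Test: two-sided chi-square for binary outcomes (Analysis for Clinical Outcomes).
- Alpha: 0.05 is stated for GOSE only ("assuming a type I error rate of 0.05, a two-sided alternative hypothesis, 7 degrees of freedom").

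**Assumptions**
- Alpha is 0.05 for reactions and TRALI. The Interim Analyses paragraph splits alpha into 0.025 per look, but it concerns 24-hour mortality and its reach is unclear. A smaller alpha would lower every power below.
- Event rates are illustrative, from 1% to 10% in the lower-rate arm.
- The chi-square is uncorrected, and all 50 patients per arm are evaluable.

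**Step 1. The plan's own power figure (GOSE).** Noncentrality = N × w² = 100 × 0.3788² = 14.35. The 5% critical value of chi-square on 7 df is 14.07. The power from the noncentral chi-square is 0.7999, so the stated 80% reproduces. It is the only power figure in the plan.

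**Step 2. Power of the planned test for rare binary outcomes.** Power = Σ Bin(a; 50, p₁) × Bin(b; 50, p₂), summed over all tables (a, b) with chi-square p < 0.05.

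| True rates | Power | Non-significant |
|---|---|---|
| 2% v 2% | 1.3% | 98.7% |
| 1% v 2% | 1.1% | 98.9% |
| 2% v 4% | 5% | 95% |
| 3% v 6% | 9% | 91% |
| 5% v 10% | 14% | 86% |
| 10% v 20% | 30% | 70% |
| 2% v 6% | 14% | 86% |
| 2% v 10% | 38% | 62% |
| 5% v 15% | 39% | 61% |
| 10% v 30% | 73% | 27% |
| 2% v 20% | 89% | 11% |

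Fisher's exact test is more conservative: 94% non-significant at 5% v 10%, and 76% at 5% v 15%.

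**Step 3. A single table.** Take 6/50 v 1/50, a sixfold observed excess. Chi-square = 100 × (6×49 − 1×44)² / (50 × 50 × 7 × 93) = 6,250,000 / 1,627,500 = 3.840, which gives p = 0.05004, just non-significant. The Newcombe 95% CI for the difference is -0.6 to +21.9 points.

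**Step 4. What an interval shows when events are few.** The Newcombe interval combines the Wilson limits of the two arms. For 0/50 the Wilson upper limit is z²/(n + z²) = 3.841/53.841 = 0.0713.

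| Observed | 95% CI for the difference (points) |
|---|---|
| 0/50 v 0/50 | -7.1 to +7.1 |
| 1/50 v 1/50 | -8.7 to +8.7 |
| 3/50 v 0/50 | -2.1 to +16.2 |

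In the first row the chi-square statistic is not even defined, since its denominator contains the total number of events. The interval still says what has not been ruled out.

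**The case against.** Two stronger readings are tempting, and the documents support neither.

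A reader might infer that the test is bound to be non-significant whatever the truth. That depends on event rates, which the documents do not give. A low rate cannot be taken from the definitions either: TRALI is mild ARDS within 6 hours of any blood product, and any transfusion complication in the first 24 hours counts as a reaction. Step 2 shows that power rises to 73% at 10% v 30% and 89% at 2% v 20%. The low-power statement is therefore conditional on low rates and moderate contrasts.

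A reader might also infer that the trial plans to declare comparable safety when p exceeds 0.05. No section says so. The gap is that no rule is given for judging the hypothesis, which leaves that reading open without prescribing it.

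Importance is limited as well. This is a 100-patient pilot with feasibility as the primary outcome, GOSE as the principal secondary outcome and 24-hour mortality as the primary safety outcome. Adverse events are reviewed for changes in nature, severity or frequency, and a DSMB weighs risk against benefit. All of this stands and lowers the practical harm. None of it supplies an analysis that addresses the hypothesis of similar rates.

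**Conclusion.** The point holds as a mismatch between a stated hypothesis and its stated analysis. That part rests on the text alone and needs no assumption about rates: a non-significant test of difference cannot support similarity.

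The numerical part is conditional. With 50 per arm, alpha 0.05 and base rates of 1% to 5%, a true doubling of risk would go undetected in about 86% to 99% of trials. Large contrasts have a fair chance of detection. Whatever the p-value, a trial with no events in either arm would still leave an excess of about 7 points not ruled out. The matter is worth correcting before analysis, but it does not touch the feasibility objective or the GOSE comparison.

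**What to change.** In Analysis for Clinical Outcomes, treat allergic/transfusion reactions and TRALI separately from the other binary outcomes:
- Make the per-arm rates and the risk difference with a 95% score-type CI the main analysis. Newcombe is one suitable choice.
- Report the upper limit as the excess risk with CSP that the trial has not ruled out.
- State that similarity will not be inferred from a non-significant test.

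In the hypothesis paragraph under Specific Aims, reword so that these two rates are to be estimated and compared rather than hypothesised to be similar. Changing the analysis alone would leave the word without a criterion. Keeping it as a hypothesis would need a justified margin, together with an acknowledgement that 100 patients cannot exclude small excesses.

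The cost is wording in two places, with no extra patients or data. The downside is a more modest safety statement at the end of the trial.
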